5.7 Efficacy Analysis

Although all efficacy analysis for this study is to be regarded as essentially exploratory, there will be formal hypothesis tests (Arm B only).

For Arm B, the data relating to efficacy response will be listed and summarized by time point, as appropriate.

For Arm C, the data relating to time to progression will be summarized/analyzed and listed by time point, as appropriate.

5.7.1 Normality assumption checking

Not Applicable (NA).

5.7.2 Closed testing procedure for primary analysis

As the analyses of the efficacy endpoints are essentially exploratory in nature no adjustments for multiple comparisons will be made.

5.7.3 Method of analysis for efficacy outcome

5.7.3.1 Objective Response Rate (ORR)

Response criteria for target lesions and non-target lesions (see [Section 3.2](#)) will be evaluated at each disease assessment and will be presented in a data listing by subject.

In addition, the presence/absence of new lesions will be collected at each disease assessment and will be presented in a data listing by subject.

The investigator will evaluate the target/non-target lesion response criteria and status (presence/absence) of new lesions against the RECIST Version 1.1 criteria to determine overall response for the appropriate disease assessment time point.

Although all efficacy analysis for this study is to be regarded as essentially exploratory, there will be a formal hypothesis test for the objective response rate here (Arm B only). Specifically, for a given disease assessment time point we denote subjects who achieve a CR or a PR Best overall response. The null hypothesis is that the proportion of objective responders (i.e., the ORR) is less than or equal to 5%. The alternative hypothesis is that the proportion of objective responders is greater than 5%. The binomial test will be used to conduct the hypothesis test at the one-sided significance level of 0.2.

Overall response and the ORR will be presented within a data listing by subject and time point.

Best overall Response (BOR) will also be listed.

The number and percentage of each BOR class will be described by cohort.

Moreover, the Sum of Target Lesion Measurements (STLM) will be analyzed from relative changes from baseline and graphically displayed with waterfall plot in order to visualize changes in sum of lesion without differentiating best response categories.

Best response to therapy will be defined as the Best Changes from Baseline in Sum of Target lesions measurement for a patient during the study.

The Best Percentage change in STLM will be calculated as, $STLM = 100 * (\text{Value of STLM} - \text{Baseline value STLM}) / \text{Baseline value STLM}$;

In case of several post baseline assessments of STLM the one with the lowest change (i.e., showing the best diminution of sum of lesions relative to baseline) will be considered.

5.7.3.2 Time to progression (TTP)

For Arm C only, the TTP will be calculated as the time from first administration of BGB324 or Erlotinib to either progressive disease as follows:

$$TTP \text{ (in months)} = [(\text{Date of event} - \text{date of first administration}) + 1] / 30.4375$$

For censored participants, the TTP will be calculated as follows:

$$TTP \text{ (in months)} = [(\text{Censored date} - \text{date of first administration}) + 1] / 30.4375$$

TTP will be analyzed descriptively for Arm C patients.

The Kaplan-Meier approach will be used to estimate TTP. The number and percent of subjects with progression, number and percent of subject censored, and median time to progression – along with its corresponding 95% confidential Interval – will be presented.

Kaplan-Meier Survival curves will be presented for TTP.

5.8 Safety Analysis

No formal statistical analysis will be performed on safety data. Summary statistics by treatment groups and timepoint will be produced.

The safety endpoints will consist of treatment-emergent adverse events, serious adverse events, physical examinations, vital signs, ECOG, ECG, Echocardiograms, and laboratory tests (clinical chemistry, hematology and urinalysis).

5.8.1 Adverse events

The AE reporting period will begin following the first dose of BGB324 (Run-in Cohort) or erlotinib (Arms A, B and C) and will end 28 days after the last dose of BGB324.

The number and percentage of patients reporting TEAEs will be tabulated by Medical Dictionary for Regulatory Activities (MedDRA) preferred term and system organ class, and summarized by CTCAE grade and relationship to study drug. All AEs commencing prior to dosing with study medication will be excluded from the tabulation but will be fully listed.

A subject with more than one occurrence of the same adverse event in a particular system organ class will be counted only once in the total of those experiencing adverse events in that particular system organ class. If a subject experiences the same adverse event at more than one severity, or with more than one relationship to study drug, the most severe rating or the stronger causal relationship to study drug will be given precedence. For example, if the event of multiple occurrences of the same adverse events being reported by the same subject, the maximum intensity (Grade 5 > Grade 4 > Grade 3 > Grade 2 > Grade 1 > missing > not applicable) and the most serious causality (related > not related) will be chosen.

Any missing severity, causality, or outcome will not be imputed and classed as unknown.

An overall summary classifying subjects with events according to seriousness, severity, maximum relationship to BGB324, and maximum CTCAE grade will also be presented.

Related events are defined as events that are ticked as suspected by investigator in eCRF .

Treatment-Emergent AEs are any AEs that start or worsen after first dose of study drug regardless of causality. AEs with partial onset dates will be assumed to have the latest possible onset date (while accounting for stop date) for determining treatment emergence, but no formal imputation will be done. AEs that have missing onset dates will be considered to be treatment-emergent, unless the stop date is known to be prior to the first administration of study drug (BGB324 or Erlotinib whichever comes first).

5.8.1.1 Subsets

- Related (BGB324) adverse events will be presented by treatment, system organ class and preferred term.
- Related (Erlotinib) adverse events will be presented by treatment, system organ class and preferred term. (Arm A, Arm B and Arm C).
- Serious adverse events will be presented by treatment, system organ class and preferred term as:
 - Related (BGB324) serious adverse events will be presented by treatment, system organ class and preferred term.
 - Related (Erlotinib) serious adverse events will be presented by treatment, system organ class and preferred term.
 - Serious adverse events will be presented by treatment group, system organ class, preferred term, and maximum CTCAE grade.
- Adverse events leading to discontinuation will be presented by treatment group, system organ class and preferred term.

- Adverse events \geq Grade 3 will be presented by treatment group, system organ class and preferred term.
- The most frequent MedDRA preferred terms ($\geq 10\%$ subjects in the overall safety population) and system organ class will be presented by treatment group.
- Separate listings will be produced for DLTs, SAEs, related AEs, discontinuations due to AEs, and events of \geq Grade 3 severity.

All other information collected (e.g. action taken) will be listed as appropriate.

Notes:

- AEs coded using MedDRA version 17.0 or above.

5.8.2 Physical Examination

Any post-baseline new or worsened physical examination findings during the safety evaluation period will be recorded as AEs and summarized in terms of AEs as described in [Section 5.8.1](#). Both the complete physical examination performed at screening and the symptom directed physical examination results will be presented in data listings.

5.8.3 Vital Signs

Results for systolic and diastolic blood pressure (mmHg), pulse rate (bpm), respiration rate (BREATHS/MIN), and temperature ($^{\circ}\text{C}$) will be summarized by dose cohort and scheduled visit, as well as the corresponding change from Baseline.

Weight (kg) and Height (cm) at screening will be summarized and listed with other vital signs data.

5.8.4 Eastern Cooperative Oncology Group

ECOG performance status will be summarized categorically at each scheduled visit with frequencies and percentage.

5.8.5 Electrocardiograms

Twelve-lead ECG triplicate will be collected the mean of the values will be analysed. In case, only one assessment is collected this value will be considered, if 2 or 3 assessments are performed the mean of available should be calculated.

The quantitative ECG assessments (PR interval (ms), RR interval (ms), QRS Duration (ms), QT interval (ms), and QTcF interval (ms)) will be summarized for actual values and change from Baseline to each visit/timepoint will be also presented.

ECG overall interpretation (normal, abnormal not clinically significant and abnormal clinically significant) will be presented as a categorical summary by treatment groups and scheduled visit.

Any post-baseline new or worsened echocardiogram findings during the safety evaluation period will be recorded as AEs and summarized in terms of AEs as described in [Section 5.8.1](#).

All echocardiogram data, including MUGA scan results will be presented in a data listing.

5.8.6 Laboratory findings

Results from the following laboratory parameters, recorded at scheduled visits, will be presented in listings:

Hematology:

Hemoglobin, Hematocrit, Red Blood Cells (RBC), White Blood Cells (WBC), Absolute Neutrophil Count, Neutrophils, Eosinophils, Basophils, Lymphocytes, Monocytes and Platelets.

Coagulation:

Prothrombin Time (PT), Activated Partial Thromboplastin Time (APTT), International Normalized Ratio (INR), and Quick Test.

Chemistry:

Sodium, Potassium, calcium, chloride, magnesium, phosphorus, creatine phosphokinase (CPK), creatinine, total protein, total bilirubin, albumin, alkaline phosphatase (ALP), aspartate aminotransferase (AST), alanine aminotransferase (ALT), glucose, uric acid, blood urea nitrogen (BUN), Bicarbonate (CO₂), electrolytes, amylase and lipase (during screening ONLY).

Urinalysis:

pH, semi-quantitative "dipstick" evaluation of Proteins, Glucose, Ketones, Blood, Nitrite, Leukocytes, Bilirubin, Bacteria, Casts, Crystals, RBC, and WBC.

Numeric Hematology and Chemistry parameters will be summarized along with each corresponding Change from Baseline for all scheduled visit by dose cohort. The incidence of laboratory test results outside the normal range will be listed by dose cohort and time point.

Clinically significant treatment-emergent laboratory findings will be summarized as adverse events.

Notes:

- All results outside predefined normal ranges will be flagged in the data listings.
- Repeat laboratory results within a visit will not be used in any summary calculations. Unscheduled and repeat results will be listed only
- Serum Pregnancy Test results will be listed.
- All other laboratory results will be listed only.

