10.1.8 Visit schedule while on corticosteroids

Patients receiving BGB324 who require the support of prednisolone (or equivalent) at 10mg to 40mg daily should be monitored at weekly intervals whilst receiving steroid treatment until the steroid dose is 10mg or less daily or is stopped.

Patients will be requested to return weekly at which time the following assessments will be undertaken:

- Physical examination
- Vital signs
- Clinical chemistry, hematology
- AE reporting/concomitant medication reporting

Patients who require daily steroids of more than 40mg prednisolone (or equivalent) should interrupt BGB324 until the steroid dose is 40mg or less daily.

Steroid restrictions do not apply to topical/ inhaled/ eye or nasal drops.

If required, additional advice on the concomitant use of steroids with BGB324 should be obtained from the BerGenBio Medical Monitor

Patients who are already attending weekly visits for C1 and C2 do not require additional visits.

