14.2.2 Methods of analysis

No formal statistical analysis will be performed on safety data. AEs will be coded using the Medical Dictionary for Regulatory Activities (MedDRA) Version 15.0 or above. The number and percentage of patients reporting treatment-emergent AEs will be tabulated by preferred term, system organ class and dose cohort, and further summarized by both CTCAE grade and relationship to study drug. All AEs commencing prior to dosing with study drug will be excluded from the tabulation but will be fully listed. AEs that have missing onset dates will be considered to be treatment-emergent, unless the stop date is known to be prior to the first administration of BGB324.

Separate listings will be produced for DLTs, SAEs, discontinuations due to AEs, and events of \geq Grade 3 severity.

Summary statistics by dose cohort and time point will be produced for vital signs, 12-lead ECG parameters and laboratory safety data, together with changes from baseline. The incidence of laboratory test results showing shifts of more than one CTCAE grade will be summarized

by dose cohort, time point and overall. Laboratory test results outside the normal range will be individually listed for clinical review, including clinical significance and the baseline value. Abnormal ECG results will be summarized by dose cohort. Changes in continuous parameters will be analyzed according to administered dose.

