5.14 Changes in Conduct or Planned Analyses from the Protocol

There have been no other changes in analyses from those defined in the protocol.

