6.1.3.2 Laboratory results

Table 14.3.5.1.1	Laboratory Results – Hematology - Summary and Change from Baseline (Safety Population)
Table 14.3.5.2.1	Laboratory Results – Coagulation - Summary and Change from Baseline (Safety Population)
Table 14.3.5.3.1	Laboratory Results –Chemistry - Summary and Change from Baseline (Safety Population)
Table 14.3.5.4.1	Laboratory Results for subjects with CTCAE \geq Grade 3 (Safety Population)
Table 14.3.5.4.2	Laboratory Results CTCAE Grade ≥ 3 (Safety Population)

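### Laboratory safety tables: Grade ≥3 values seen only on unscheduled or repeat samples can be missed, and the protocol's CTCAE shift summary is separately dropped without being declared

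*SAP*

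**What the plan says.** **Unscheduled and repeat values.** SAP 5.8.6 has two adjacent sentences. On repeats: "Repeat laboratory results within a visit will not be used in any summary calculations". On unscheduled and repeat results together: "Unscheduled and repeat results will be listed only". The descriptive summaries are tied to planned visits: "Numeric Hematology and Chemistry parameters will be summarized along with each corresponding Change from Baseline for all scheduled visit by dose cohort".

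**Grade ≥3 tables.** SAP 6.1.3.2 plans Tables 14.3.5.4.1 (title beginning "Laboratory Results for subjects with CTCAE") and 14.3.5.4.2. Only titles are given. Neither there nor in 5.8.6 is there a derivation rule, a worst-post-baseline definition or an exception to the listed-only note.

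**Shift summary.** Protocol 14.2.2 states: "The incidence of laboratory test results showing shifts of more than one CTCAE grade will be summarized", for each dose cohort, at each time point and overall. At the corresponding place SAP 5.8.6 has a listing: "The incidence of laboratory test results outside the normal range will be listed by dose cohort and time point". SAP 5.14 then says: "There have been no other changes in analyses from those defined in the protocol".

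**Steroid monitoring.** Protocol 10.1.8 adds weekly chemistry and hematology for patients on 10 to 40 mg prednisolone daily (or equivalent): "Patients will be requested to return weekly at which time the following assessments will be undertaken".

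**The concern.** Safety and tolerability is the primary objective of the Run-in Cohort, Arm B and Arm C, and it underlies the choice of recommended Phase 2 dose in Arm A. Laboratory grade tables matter here because they do not depend on whether an investigator chose to report an event.

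Off-schedule samples tend to be taken when something is already suspected. The protocol anticipates this. Section 13.4.3 lists the need for more frequent follow-up among its suggested markers of clinical significance, and Section 11.3.1.3 allows an unscheduled visit in connection with potassium control and QTc risk. A rule that keeps such samples out of every table removes values that are not a random subset.

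The missing shift summary is a different problem. It is a protocol commitment that disappears without being declared, and it concerns worsening below Grade 3 as well as above it.

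**Working it through.** The plan states no figure on this point, so the check is a comparison of texts plus a count from the visit schedule.

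**1. Direction of the effect on worst grade.** A patient's worst grade is the maximum over the results used. The maximum over a subset can never exceed the maximum over the full set. Dropping unscheduled and repeat results can therefore leave a patient's worst grade unchanged or lower it, but cannot raise it. The documents do not allow an estimate of how often it would be lowered.

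**2. What one missed patient would do to a rate.** Planned maximum arm sizes (Protocol 8.1) are 6, 18, 25 and 14. One patient is:
- Run-in Cohort: 1/6 = 16.7 percentage points
- Arm A: 1/18 = 5.6
- Arm B: 1/25 = 4.0
- Arm C: 1/14 = 7.1

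These show scale only. They do not predict that a patient will be missed.

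**3. Steroid-monitoring draws.** Inputs are the 21-day cycle, chemistry and hematology on Day 1 only from Cycle 3 (Protocol Table 5), and weekly sampling while on steroids (Protocol 10.1.8).
- Weekly draws per cycle: 21/7 = 3. One coincides with the Day 1 visit, leaving 3 − 1 = 2.
- If those two count as unscheduled, 2 of 3 draws are listed only.
- If they count as scheduled, 0 of 3 are lost.
- After 12 months, routine chemistry and hematology are every 3 months (Protocol 10.1.7), about 52/4 = 13 weeks. The corresponding range is 0 to about 12 of 13.

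The SAP does not classify these visits. Section 10.1.8 calls itself a visit schedule, and footnote x places the monitoring in both schedules of events, which suggests scheduled. As read from the PDF, however, the footnote marker sits on Weeks 1 to 6 and not on the later column. Section 10.1.8 also says that patients already attending weekly in Cycles 1 and 2 need no additional visits, which implies that later ones are additional. The text supports either classification.

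**4. The shift summary.** Taking baseline Grades 0 to 2 and post-baseline Grades up to 4, the worsening shifts of more than one grade are 0→2, 0→3, 0→4, 1→3, 1→4 and 2→4, which is six. Five end at Grade 3 or 4 and so could appear in the Grade ≥3 tables, though the titles do not show whether baseline grade is given. The sixth, 0→2, ends below Grade 3.

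SAP 6.1.3.2 contains five laboratory tables: three of values and change from baseline, and two for Grade ≥3. None is a shift table, so 0→2 is counted in no laboratory grade table.

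**5. Consistency within the SAP.** Section 5.8.6 opens by describing listings of results from scheduled visits, then says unscheduled results are listed. For ECG the SAP does plan a maximum-change table (14.3.6.2.4). It states no equivalent for laboratory data.

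**The case against.** The strongest reply is that little is lost. All values remain in listings, including Listing 16.2.8.1.7 for patients with Grade ≥3 results. SAP 5.8.6 sends clinically significant laboratory findings to the adverse event tables, which include breakdowns by CTCAE grade and for Grade ≥3. Protocol 13.4.3's suggested criteria for clinical significance cover treatment changes, interventions and closer follow-up, which are largely the situations that produce extra samples. Safety analysis is descriptive, with no formal test. The listed-only note also follows text on by-visit summaries and may have been written with only those in mind.

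Much of this stands, and it rules out several stronger readings that a reader might infer:
- *Laboratory toxicity is understated.* The documents show only that it can be. The SAP gives no derivation for the Grade ≥3 tables, so the effect on them is read from a general note.
- *Two thirds of laboratory draws are lost.* That is the upper end of a range starting at zero. It applies from Cycle 3 through Cycle 17 to patients on the specified steroid doses, and a share of draws is not a share of missed Grade ≥3 results.
- *Moderate worsening appears in no summary.* Clinically significant Grade 2 findings appear in the adverse event tables, and scheduled values feed the change-from-baseline tables. The gap is in laboratory grade tables.
- *Dropping the shift table causes the Grade ≥3 gap.* It does not. The two defects are independent.

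The reply does not remove the point. The adverse event route depends on investigator judgment: the criteria are suggestions, and abnormalities clearly consistent with the disease or its progression need not be reported. A listing gives no incidence. Ad hoc and repeat samples are excluded however the steroid visits are classed.

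**Conclusion.** Two separate defects hold.

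First, SAP 5.8.6 applied literally can leave a Grade ≥3 value out of Tables 14.3.5.4.1 and 14.3.5.4.2 when it was seen only on an unscheduled or repeat sample. The possible error in worst grade runs one way, towards lower toxicity. Its size cannot be fixed from the documents: the number of off-schedule samples and of steroid-treated patients is not given, and the steroid draws contribute anything from 0 to 2 of 3 per cycle from Cycle 3 through Cycle 17. This conclusion assumes that the listed-only note governs the Grade ≥3 tables, which is the plain reading because no exception is stated.

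Second, the protocol's summary of shifts exceeding one CTCAE grade is absent from the SAP text and table list, and SAP 5.14 does not declare the omission. This rests on no assumption.

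Both should be corrected. Neither means that data are lost, since collection and listing are unaffected.

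**What to change.** 1. Keep the by-visit descriptive summaries in SAP 5.8.6 on scheduled values, and limit the listed-only note to them.
2. Define worst post-baseline CTCAE grade, and derive it and Tables 14.3.5.4.1 and 14.3.5.4.2 from all post-baseline results, including unscheduled and repeat values.
3. Restore the Protocol 14.2.2 table of shifts exceeding one CTCAE grade for each dose cohort, at each time point and overall. The overall (worst-value) shift should use all post-baseline results. If the table is not restored, declare and justify its removal in SAP 5.14.
4. State whether the weekly samples under Protocol 10.1.8 count as scheduled for the by-visit summaries. Align the opening sentence of SAP 5.8.6 with its note on unscheduled results.

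The cost is SAP wording and one additional table. No new data are needed. Laboratory toxicity rates may look slightly worse.

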5.9 Pharmacokinetic Analysis

The Pharmacokinetic (PK) Analysis will be conducted separate by BergenBio from this analysis. Details will be found in a specific analysis plan. Subjects included in PK population can be identified in the clinical datasets.

5.10 Pharmacodynamic Analysis

The Pharmacodynamic Analysis will be conducted separate from this analysis. Details will be found in a specific analysis plan.

5.11 Protocol Deviations

Deviations from the protocol will be documented on an ongoing basis by the study monitors and project manager throughout the study period.

At the time of database lock, prior to unblinding and while the protocol deviations are being reviewed, the project manager will forward all relevant documentation highlighting protocol deviations to the study statistician. These deviations will be included in the protocol violation document for agreement and will be listed with the protocol violations in the CSR.

